We hypothesize that, compared to untreated controls, EPO therapy in anemic patients with CKD will raise diastolic blood pressure. The magnitude of the increase in diastolic BP at 12 weeks after treatment will be related to endothelial dysfunction and worsening of endothelial function from baseline to 4 weeks. The factors underlying endothelial dysfunction will be explored by interrogating the nitric oxide pathway (24h urine nitrate and nitrite and plasma ADMA), endothelin activation (plasma endothelin 1 concentration), and changes in the renin angiotensin system (seated plasma aldosterone, renin activity, and 24h urine sodium excretion rate). We will use a randomized controlled trial design with open-label administration of EPO to 80 patients in each group and comparison of the responses over 12 weeks of treatment. The dispensing of EPO will depend on which group the participant is randomized to. The immediate start group will be given EPO at randomization and diastolic BP will be assessed after the first 12 weeks of treatment. While the untreated “waitlisted” controls will be treated with EPO after 12 weeks. We then will examine the diastolic BP after an additional 12 weeks of treatment with EPO. Oral iron will be used in both groups to replete iron deficiency, if necessary given lab work. We will observe the relationship between diastolic BP and endothelial dysfunction using paired testing with each subject’s baseline results serving as their own control. Preliminary data show that our sample size has the ability to detect 5 mmHg change in diastolic BP between groups. For endothelial dysfunction, most studies are powered to detect 1-2% change from baseline.

BACKGROUND

Hypertension is believed to be a common adverse effect of EPO therapy ¹⁻⁶. However, the incidence and severity of EIH is difficult to quantify because underreporting of hypertension is common. Underreporting is likely due to 3 reasons: (i) more aggressive management of hypertension through prescription of antihypertensive drugs, (ii) among dialysis patients, closer attention to dry-weight ^{19,20} and (iii) lack of precise quantification, such as by ABPM ²¹. We have conducted a cross-sectional survey

of hemodialysis patients using 44-hour interdialytic ambulatory BP monitoring to conclusively demonstrate that EPO therapy is indeed an independent determinant of hypertension ²².

Importance of CKD in EPO-induced hypertension

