	UACR (x3)		x	x	x	x	DS	DS	DS
	Biomarkers		x	x		DS	DS		
Group	Immediate Start		x	x	x				
	Delayed Start		x	x	x	x	x	x	x

*CBC, Renal Panel, Ferritin, TSAT

** V1 if consent: CBC & eGFR panel

DS = Delayed Start ONLY

This is a two-arm, open-label, single-center, randomized controlled trial to understand the mechanisms of EIH. Participants will be randomized based on stratum of baseline level of urine albumin/urine creatinine ratios (UACR) measured on three consecutive days. The primary analysis will compare the 80 participants in the early start group to the 80 in the delayed start (DS) or waitlisted group over the first 12 weeks. All procedures will be performed as listed in the table based on study visit. Confirmatory analysis will compare the first 12 weeks to the next 12 weeks in the DS group. Accordingly, the study procedures labeled DS will be performed only in the delayed start randomized participants.

Study Intervention

Participants with CKD and anemia who meet the inclusion and exclusion criteria will be randomized to either the immediate or delayed start group. There are at least 7 study related visits in the early start group, and 11 in the waitlist group. Two consecutive days are needed to perform 24h ambulatory BP monitoring, which will be done twice in the immediate start group and 3 times in the delayed start group. Patients will receive oral iron (ferrous sulfate, 324 mg orally twice daily) if serum ferritin concentration is <100 ng/mL or transferrin saturation is <20%. If clinic BP exceeds either 179 mmHg systolic or 109 mmHg diastolic or if clinic BP raises by >20/10 mmHg compared to baseline, antihypertensive medication dose will be increased or a new antihypertensive will be added.

Participants will be identified in the renal clinic or the electronic medical record system based on estimated GFR and Hgb. At baseline, all participants will have 24-h urine Na measured to assess dietary Na intake.

Treatment Adherence

We recognize the limitations of syringe count, but we will assess treatment compliance with the study drug by performing a syringe count at each of the study visits.

Protocol for the management of anemia

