Harms will be assessed by monitoring changes in weight, eGFR, CBC, clinic BP, and ABPM. For more definitive assessments, including hospitalizations, serious adverse events will be properly completed and sent to the VAMC DMC as requested. Safety of continued participation will be assessed at each study visit. The stop-points will be treatment-emergent severe adverse events that precludes further exposure to the drug, such as an allergic drug reaction, initiation of renal replacement therapy, or death. If the study drug is stopped, the subject will be continued to be studied so as to not violate the intention-to-treat principle.

Participants

Inclusion Criteria

- Stage 3 or 4 CKD defined as eGFR <60mL/min/1.73m² for ≥3 months or persistent albuminuria for ≥3 months; (i) urine albumin to creatinine ratio of more than 30 mg/g; (ii) urine protein to creatinine ratio of more than 150 mg/g; or (iii) at least 1+ dipstick positive proteinuria. ⁸⁸
- 24h ABPM <140/90 mmHg at baseline in the presence or absence of antihypertensive treatment.
- Hgb between 8 and 10 g/dL.
- No treatment with ESA within the previous 3 months.
- Adults, age 18 and older.

Exclusion Criteria

- Need for packed RBC transfusion in the previous 2 months.
- Myocardial infarction, stroke, or hospitalization for heart failure in the past 2 months.
- In the assessment of the investigator, have hematologic, inflammatory, infectious, or other conditions that might interfere with the erythropoietic response.

Retention of Participants

For half of the participants, only 7 visits are needed. For the others, at least 11 visits over 24 weeks of the trial are needed. We will offer \$20 per visit for participation in the trial to offset travel and time costs.

METHODS

Method of Randomization

Participants will be randomized in a 1:1 ratio to either early or delayed treatment (“waitlisted group”) with EPO according to UACR strata. A random permuted block design will be used to avoid imbalance in assignment to the treatment groups over time. A randomization sequence will be generated by the statistician and individually concealed in sequentially numbered opaque envelopes. After confirming eligibility with the principal investigator, the study pharmacist will dispense EPO according to the randomization sequence.

Measurement of clinic BP

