Longitudinal resting images will be acquired before inflation. Blood flow estimated by the pulsed Doppler velocity signal using the outer envelope technique to calculate the velocity time integral will be obtained from a mid-artery sample volume at baseline and upon immediate cuff release to assess hyperemic velocity. Peak hyperemic velocity will be determined from the first complete velocity envelope after cuff release. Higher values of hyperemic velocity represent better microvascular dilatation ⁹³. Longitudinal images of the artery in B mode will be continuously recorded for 3 min after cuff deflation. Images will be recorded digitally using an R-wave gated digitizing interface external to the machine (MIA- LLC, Coralville, IA).

A few minutes after deflation, another image will be acquired to reflect a reestablished baseline. The above procedure is repeated to acquire the images in

deviation of 0.93% and between-subject standard deviation of 1.77%. Thus, the test-retest coefficient of variation was 7.2% in our laboratory.

Biomarker measurements

We may use specimen collected as part of this study for analysis of DNA which may include whole genome sequencing. Plasma endothelin-1 will be measured using validated ELISA kits (R&D systems, Inc., Minneapolis, MN). 24h urinary nitrite and nitrate and total nitrates will be measured using the Greiss reaction using kits from R&D systems, Inc. Renin and aldosterone will be measured using a commercial laboratory (LabCorp, Burlington, NC). Plasma ADMA will be measured using LCMS in our biochemistry core lab. The usual labs such as blood counts, chemistries, urine albumin and Na will be measured in the hospital laboratory. Renin + aldosterone lab testing will require the participants to be resting in seated position for at least 15 minutes prior to blood draw.

STATISTICAL METHODS

Outcome Variables

The outcome variables are as follows:

1. Change from baseline to 12 weeks in diastolic BP in EPO treated patients compared to delayed start controls. In the waitlisted group, we will measure the change from 12 weeks to 24 weeks compared to the change from 0 to 12 weeks.

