2. Change from baseline to 12 weeks in systolic BP in the comparisons above. Between group change in hypertension status from baseline to 12 weeks. Worsening of hypertension at any time point will be defined either as an increase in BP medication or an increase in seated clinic diastolic BP of ≥ 10 mmHg or systolic BP ≥ 20 mmHg. Within-group change in hypertension status from 12w to 24 w will be compared to the control period of 0 to 12w in the delayed start group.
3. The primary outcome variable in this aim is to examine the change in FMD from baseline to 4 weeks in those treated with EPO compared to the waitlisted group. The hypothesis being tested is that EPO will cause impairment in endothelial function. Accordingly, those on EPO will have worsening of FMD.
4. The primary outcome variable in this aim is to examine the predictors of change in FMD from baseline to 4 w in those treated with EPO compared to time controls. Predictors of this change will be baseline values of the following variables: ADMA, urine nitrate and nitrite, renin, aldosterone, and plasma endothelin-1 and change from baseline to 4 w in the above variables. This analysis will answer the question: which of the pathways independently is predictive of endothelial dysfunction?

Sample Size

The primary objective of the study is to assess the change from baseline to 12 weeks in diastolic BP in EPO treated patients compared to controls. In the waitlisted group, we will measure the change from 12 weeks to 24 weeks compared to the change from 0 to 12 weeks. We have measured 24h

ambulatory BP in 183 CKD patients 4 weeks apart. The mean diastolic BP at baseline was 68.3 mmHg and at 4 weeks 68.1 mmHg. The mean difference was 0.14 mmHg and the standard deviation of the difference was 10.3 mmHg. With these assumptions, two-tailed tests and 80% power, the required sample size to detect a between-group difference of 5 mmHg is 68 subjects completing the study in each group. Assuming 85% of those randomized complete the trial, we would need to randomize $68/0.85 = 80$ subjects per group, or 160 subjects in total.

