outcome variable controlling for the group assignment (β_i is significant in [C] and $\tau' < \tau$, which provides evidence for mediation rather than suppression); and (4) the mediated effect is statistically significant. For mediators that satisfy conclusions 1 through 3, the significance of mediation (conclusion 4) will be determined via interval estimation of the mediated effect using the asymptotic variance derivation of Sobel ⁹⁸ since the outcomes are the continuous measures. Additional analyses that look at thresholds of change (binary: worsening of hypertension or not) will utilize bootstrapping methods and logistic regression. The proportion of the effect mediated is calculated as the ratio of the indirect effect to the total effect, or $\alpha\beta/\tau$.

The primary outcome for flow-mediated dilatation is change in FMD from baseline to 4 w in those treated with EPO compared to time controls. Predictors of this change will be baseline values of the following biomarkers: plasma ADMA, urine nitrate and nitrite, and plasma renin, aldosterone, and endothelin-1 and change from baseline to 4 w in the above biomarkers. In addition, the baseline FMD will be an independent variable. This analysis will use regression models similar to the above-listed analyses.

Pre-specified sub-group analyses for BP response

- Effect of age: The effect of age (e.g., 65 or more and <65) will be tested using interaction effects.
- Effect of volume overload: Volume overloaded subjects are more likely to show worsening EIH with EPO therapy. In people with volume overload, renin and aldosterone levels are expected to be low and 24-hour urine Na high. We will dichotomize the baseline levels of these markers and examine the outcome on ambulatory BP using interaction effects.

Safety analysis

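### Baseline renin and aldosterone are read as volume status and as pathway activity without any account of antihypertensive drug class

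*Combined protocol and SAP*

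**What the plan says.** **Who is enrolled.** The inclusion criteria require "24h ABPM <140/90 mmHg at baseline in the presence or absence of antihypertensive treatment". Neither the inclusion nor the exclusion criteria restrict any antihypertensive class. Under Study Intervention, once clinic BP passes a trigger, "antihypertensive medication dose will be increased or a new antihypertensive will be added", with no class named.

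**How the assays are taken.** Biomarker measurements gives one condition: "Renin + aldosterone lab testing will require the participants to be resting in seated position for at least 15 minutes prior to blood draw". Drug use at the draw is not mentioned.

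**First use, volume status.** Under Pre-specified sub-group analyses for BP response, the plan expects more EPO-induced hypertension in volume-overloaded patients and identifies them by the pattern "In people with volume overload, renin and aldosterone levels are expected to be low and 24-hour urine Na high". It continues: "We will dichotomize the baseline levels of these markers and examine the outcome on ambulatory BP using interaction effects". It gives no cut-point and no rule for combining the three markers.

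**Second use, pathway activity.** Outcome Variables, item 4, says of change in FMD: "Predictors of this change will be baseline values of the following variables: ADMA, urine nitrate and nitrite, renin, aldosterone, and plasma endothelin-1", together with the 4-week changes in the same markers. The aim is to learn "which of the pathways independently is predictive of endothelial dysfunction". The FMD paragraph of the analysis section repeats the list and adds baseline FMD as a covariate.

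**Where medication enters.** BP medication appears in the analysis plan only as a component of the worsening-of-hypertension outcome. It is not a covariate, stratum or sensitivity factor in any model.

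**The concern.** Converting-enzyme inhibitors and receptor blockers raise renin and tend to lower aldosterone, beta-blockers mainly lower renin, and diuretics raise both. This is general pharmacology that the documents do not state. In a CKD population admitted with or without antihypertensive treatment, a high/low split of either assay therefore reflects drug use as well as volume. Under a renin-system blocker the two markers also disagree: high renin says not overloaded, low aldosterone says overloaded.

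There are two consequences for the subgroup analysis.

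- **Dilution.** If volume does modify the EPO effect, a drug-driven label weakens the test. This needs no further assumption about how the drugs and EPO interact.
- **Misattribution.** If the EPO response differs between users and non-users of these drugs, that difference can surface as a marker interaction and be reported as a volume effect. If blocker users rise less on EPO, the low-renin half, enriched for non-users, rises more. That is the direction the plan predicts for overload.

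In the FMD regression, a drug effect on FMD change could be credited to baseline renin or aldosterone. These mechanistic conclusions are among the products of the trial, so the labels matter.

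**Working it through.** **1. The plan's own figure.** Inputs from Sample Size: SD of change 10.3 mmHg, difference 5 mmHg, two-sided, 80% power; alpha is not stated, so 0.05 is assumed.

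n per group = 2 × (1.96 + 0.84)² × 10.3² / 5² ≈ 67 (normal), 67.6 with the t distribution, hence 68; 68/0.85 = 80. The stated 68 and 80 reproduce.

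**2. What a perfect subgroup label can detect.** With 68 completers per arm and a 50/50 split (34 per cell):

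SE of interaction = 10.3 × √(4/34) = 3.53 mmHg.

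Detectable at 80% power = 3.53 × 2.80 = 9.9 mmHg. Power for a 5 mmHg interaction is about 29%, and for 10 mmHg about 81%.

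**3. How much the renin split still measures volume.** The documents give no drug-use rates or assay shifts, so these are assumptions: log renin = −0.8 × volume (standard normal) + ln(fold) × drug use; one drug class, raising renin 2- to 5-fold; 40-80% users; median split.

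- With no drug effect, the correlation of the split with volume is √(2/π) = 0.80.
- With 60% users and a 3-fold shift, users are 36% of the low-renin half and 84% of the high-renin half, and the correlation is 0.64.
- Over all settings it is about 0.51 to 0.75.

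For an effect linear in volume, the observed interaction shrinks in proportion to the correlation. A 10 mmHg interaction becomes 10 × 0.75/0.80 = 9.4, 10 × 0.64/0.80 = 8.0 or 10 × 0.51/0.80 = 6.4 mmHg. With power ≈ Φ(interaction/3.53 − 1.96), the 81% falls to about 76%, 62% or 44%.

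**4. False volume interaction when volume has no effect.** Suppose the EPO response is d mmHg smaller in drug users. At 60% users and a 3-fold shift, the two halves differ in user share by 0.84 − 0.36 = 0.48, so the apparent volume interaction is 0.48 × d. The chance of significance is approximately Φ(0.48d/3.53 − 1.96) + Φ(−0.48d/3.53 − 1.96):

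| d (mmHg) | apparent interaction (mmHg) | chance of p < 0.05 |
|---|---|---|
| 3 | 1.4 | about 7% |
| 5 | 2.4 | about 10% |
| 8 | 3.8 | about 19% |

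Simulated trials of 136 patients, analysed as change from baseline, agree:

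| users | shift | d = 5 | d = 8 |
|---|---|---|---|
| 60% | 2-fold | 7.1% | 10.6% |
| 60% | 3-fold | 11.3% | 18.2% |
| 60% | 5-fold | 13.6% | 28.4% |

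With d = 5, the rate is 6.2-6.3% for a 2-fold shift at 40% or 80% users, and 7.6% for a 3-fold shift at 80% users. Over the whole range of assumptions at d = 5-8 it is about 6-30%, allowing for simulation error. At d = 3 it is 5-9%, and at d = 0 it stays at 5%.

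**5. Effect of the repair.** Adding drug use and group × drug use to the same model brings the rate back to about 5% (4.6-6.0% in the four 3- and 5-fold cells above).

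**The case against.** **The false-positive branch needs an interaction that the documents do not support.** A 5-8 mmHg difference in EPO response by drug use is 100-160% of the 5 mmHg effect the trial is powered for. The Background section on the renin-angiotensin system reports that, in EPO-treated rats with subtotal nephrectomy, renin-system blockers lowered systolic BP no more than conventional triple therapy. It also reports that EPO increased angiotensin receptors in cultured cells despite enalapril or losartan. The same section calls the evaluation in treated CKD patients incomplete, so the interaction is not excluded. It remains an assumption, and this objection stands.

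**The model is simpler than practice.** It has one drug class moving renin upward. Adding 50% beta-blocker users with a 2-fold reduction (assumed) lowers the 3-fold, 5 mmHg rate to 8.5%; adding unrelated log-renin noise with SD 0.5 instead gives 9.2%. Aldosterone was not simulated and the FMD regression has no calculated magnitude. This also stands.

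**There is a third marker.** Disagreement among renin, aldosterone and urine Na could itself reveal a drug artefact. This is fair, but the plan has no rule for reading them together, and Study Intervention describes urine Na as a measure of dietary intake, so it does not settle volume status.

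**The FMD regression also uses 4-week changes.** A stable regimen largely cancels out of a within-person log change, so the concern there falls mainly on baseline values.

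**Adjustment can go too far.** Diuretics may be prescribed because of volume overload, so requiring the marker interaction to survive a diuretic interaction could remove the effect sought. This limits the fix.

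**Stronger readings.** A reader might infer that the low-renin subgroup is simply a drug-use subgroup, or that a false volume finding is likely. Without drug-use rates or evidence of a drug-by-EPO interaction, the documents support neither.

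**Conclusion.** The concern holds as a limit on interpretation. As written, the plan can credit a difference linked to drug class to volume overload or to the renin-angiotensin pathway, and it has no term that would show this.

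The better-supported consequence is dilution: under the assumed shifts and user rates, the correlation of a renin split with volume drops from 0.80 to about 0.51-0.75, in an analysis that at best detects 9.9 mmHg. The false-positive rate of about 6-30% is conditional on an undocumented 5-8 mmHg difference in EPO response between users and non-users; at 3 mmHg or less it is near nominal.

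A reader might also infer that the EPO effect on BP is biased. It is not. Randomisation protects the EPO versus waitlist contrast overall and within each half of a baseline split, and the primary analysis does not use these markers. What is at risk is the explanation given for a difference between the halves.

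**What to change.** 1. Record baseline use (yes/no) of renin-system blocker, beta-blocker, diuretic and mineralocorticoid antagonist.
2. In the renin and aldosterone volume-overload models, add renin-system-blocker and beta-blocker use and their interactions with group. In the mixed-model form, this includes the group × time × drug terms beside group × time × marker.
3. Add diuretic and mineralocorticoid-antagonist terms only as a sensitivity analysis, because these drugs may themselves mark volume overload.
4. Add the drug indicators as covariates in the FMD-change regression, and state that the concern there is mainly with the baseline marker values.
5. Report the urine Na interaction beside those for renin and aldosterone. Attribute effect modification to volume only if the renin or aldosterone interaction persists with the renin-system-blocker and beta-blocker terms in the model; otherwise label it exploratory.

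**Cost.** SAP wording and one baseline data item. No section describes a baseline drug-class record, but medication has to be tracked to score an increase in BP medication, so the extra work should be small. On the change scale, step 2 uses four degrees of freedom out of about 136 completers, in an exploratory analysis that already has low power. Treatment, eligibility and visits do not change.

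### Baseline renin, aldosterone and urine sodium are split at unstated cut-points before the volume-overload interaction test, so the result depends on the cut and loses power if the modification is roughly linear

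*Combined protocol and SAP*

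**What the plan says.** In the combined protocol and SAP, the section Pre-specified sub-group analyses for BP response has two items: age and volume overload. For the second, the plan expects that in volume overload "renin and aldosterone levels are expected to be low and 24-hour urine Na high", and that such patients will show more EPO-induced hypertension. The method is one sentence: "We will dichotomize the baseline levels of these markers and examine the outcome on ambulatory BP using interaction effects".

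No cut-point is given for any of the three markers, and no rule for combining them. The age item at least offers 65 years as an example. Neither of the two mixed models under Primary Analysis contains a marker term. The regression for flow-mediated dilatation (FMD) does use baseline renin and aldosterone ("Predictors of this change will be baseline values of the following biomarkers"), with no split stated, but its outcome is FMD, not BP. The Sample Size section gives no power for any subgroup test.

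**The concern.** All three markers are continuous laboratory values. Splitting them raises two problems.

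- **The cut is open.** The answer can change with the cut. In an open-label trial with three markers and no stated cuts, nothing prevents the choice from being made after the data have been seen. This holds whatever the true relation between marker and response.
- **Information may be discarded.** If the EPO effect changes roughly linearly with the marker, treating everyone on one side of the cut as alike lowers power. An interaction test in a trial sized for a main effect has little to spare.

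At stake is the interpretability of one pre-specified subgroup question about who is prone to EPO-induced hypertension.

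**Working it through.** **Inputs**
- SD of change in 24-hour diastolic BP, from Sample Size: "The mean difference was 0.14 mmHg and the standard deviation of the difference was 10.3 mmHg".
- Target and size, same section: "With these assumptions, two-tailed tests and 80% power, the required sample size to detect a between-group difference of 5 mmHg is 68 subjects" per group. "Assuming 85% of those randomized complete the trial", so 80 are randomized per group.
- Allocation, from Method of Randomization: "Participants will be randomized in a 1:1 ratio to either early or delayed treatment".
- Assumed here: two-sided alpha 0.05 (the plan does not state alpha), diastolic BP as the outcome (the subgroup text says only ambulatory BP), 136 completers (2 × 68), and a median split unless stated otherwise. UACR strata are ignored.

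**Step 1: the plan's own figure.** n per group = 2 × [10.3 × (1.960 + 0.842)/5]² = 66.6, or 67 by the normal approximation. The t-test version gives 67.6, so 68. Then 68/0.85 = 80. The plan's size is reproduced, which supports the assumed alpha.

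**Step 2: information kept by a cut.** For a normal marker with a linear effect, cut so that a fraction p lies below, the efficiency relative to the continuous marker is φ(z_p)²/[p(1 − p)]. At the median this is 2/π = 0.637, so 136 patients act like about 87.

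| Cut (normal marker, linear effect) | Information lost |
|---|---|
| 50/50 | 36% |
| 40/60 | 38% |
| 30/70 | 42% |
| 20/80 | 51% |
| 10/90 | 66% |

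The figure for a log-normal marker is the same if the effect is linear on the log scale. With a median split, a uniform marker loses about 25%. A skewed marker (log-normal, log-SD 0.5 to 1.0) whose effect is linear on the raw scale loses about 49% to 73%. If the true effect is a step exactly at the cut, nothing is lost.

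**Step 3: precision with 136 completers**
- Median split, four cells of 34: SE = 10.3 × √(16/136) = 3.53 mmHg for the difference in EPO effect between the high and low halves.
- Continuous: SE = 2 × 10.3/√136 = 1.77 mmHg per SD of marker.
- The halves of a normal marker differ by 2√(2/π) = 1.596 SD on average, so 5 mmHg high-minus-low equals 3.13 mmHg per SD.

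**Step 4: power and detectable difference**
- Split, 5 mmHg: Φ(5/3.53 − 1.96) = 29%.
- Continuous, same truth: Φ(3.13/1.77 − 1.96) = 43%.
- Detectable at 80% power, split: 2.80 × 3.53 = 9.9 mmHg.
- Detectable at 80% power, continuous: 2.80 × 1.77 = 4.9 mmHg per SD, and 4.95 × 1.596 = 7.9 mmHg high-minus-low.
- If all 160 complete, power for 5 mmHg is 34% split and 49% continuous.

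**Step 5: simulation (5,000 trials per setting, 136 patients)**

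| True modification | High-minus-low | Power, split | Power, continuous |
|---|---|---|---|
| None | 0 | 5% | 5% |
| Linear | 5 mmHg | 29% | 41% |
| Linear | 10 mmHg | 77% | 93% |
| Step at median | 5 mmHg | 27% | 18% |
| Step at median | 10 mmHg | 81% | 60% |

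**The case against.** The strongest reply is that the plan does not state a graded hypothesis. It speaks of patients who are volume overloaded as a category and uses the markers as indicators of that state. If overload acts as a switch and the cut falls at the switch, the split is the better test, as the last two simulated rows show. This stands, and it makes the efficiency loss conditional. But the plan does not argue for a threshold or say where one would lie, and a split at an unspecified point has no claim to match it.

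A second reply is that this is one secondary subgroup item. The main mechanistic analyses are the mediation models and the FMD regression, and the latter uses baseline renin and aldosterone with no split stated. That stands as a limit on importance, but it does not repair the BP interaction test.

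A reader might also infer that keeping the markers continuous would give a well-powered test. At 5 mmHg per SD, the SEs above imply about 81% power continuous and 62% split. But 5 mmHg per SD is 5 × 1.596 = 8.0 mmHg high-minus-low, more than the whole 5 mmHg effect for which the trial is sized. Nothing in the documents suggests an interaction that large. For one equal to the planned effect, both versions fall short of 50% power.

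**Conclusion.** The point holds as a cheap improvement to a secondary analysis. The firm part is that the split is planned, the cuts are unstated, no continuous alternative for BP exists, and the result depends on the cut chosen.

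The efficiency part is conditional. A loss of about 36% needs a marker that is normal (or log-normal on the log scale), a linear effect and a median split. A reader might infer that a third of the information is lost outright, but the plan fixes none of these conditions, and the loss ranges from none to well over half.

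Under those conditions, with SD 10.3 mmHg, 136 completers and assumed alpha 0.05, going continuous raises power for a 5 mmHg high-minus-low difference from about 29% to 43%. The detectable difference falls from about 9.9 to 7.9 mmHg. The test remains underpowered for modest interactions, so a null result should not be read as absence of modification either way. The primary comparison is untouched.

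**What to change.** In the subgroup section, replace the split with a continuous test. For each marker in turn, add it to model 1 with its interactions, and test group × time × marker. Use the log scale for renin and aldosterone. Report the change in EPO effect per SD of marker with a confidence interval. Show estimates below and above the median as display only, with that cut fixed in advance and no test attached.

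The cost is SAP wording. Baseline biomarkers and 24-hour urine are already scheduled for all participants in the Figure 2 table, so no new data, visits or patients are needed.

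The downside is that the test assumes an approximately linear relation and would be less powerful than the split if the true modification were a step at the cut. If the investigators believe in such a step, the plan should say so and give the cut and its basis before the data are examined.
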